## Abstract

Pre-diabetes affects over 325 million adults worldwide. These individuals that are predisposed to developing type 2 diabetes mellitus have few options to prevent the progression of the disease other than diet and exercise. Emerging evidence suggests that the active form of vitamin D, 1,25-dihydroxyvitamin D3 (1,25(OH)2D3; also known as calcitriol), contributes to glucose metabolism partly by increasing insulin secretion and also by increasing muscle glucose utilization. We intend to investigate the effects of a low daily dose of 1,25(OH)2D3 on glucose tolerance and muscle function in persons who are susceptible to developing diabetes. This study could provide a new strategy for preventing the progression of type 2 diabetes mellitus with a drug that is already approved for use by the US Food and Drug Administration.

## Research Plan

### A. Specific Aim

The aim of this study is to assess the effects of 1,25(OH)2D3 on insulin secretion by the pancreas and glucose utilization by skeletal muscle as well as to determine the effects of 1,25(OH)2D3 on muscle strength in pre-diabetic subjects.

Hypothesis: 1,25(OH)2D3 will increase the rate of insulin secretion by pancreatic beta cells and improve glucose uptake in muscle, resulting in improved glucose homeostasis. Secondarily, 1,25(OH)2D3 will increase muscle strength.

Approach: This will be a double blind randomized control trial in pre-diabetic persons. Each participant will be randomly assigned to receive an oral tablet containing 0.25 µg 1,25(OH)2D3 or a placebo tablet for 8 weeks. Identical assessments will be performed both before and after the 8-week intervention period. These assessments will include the 2-hour glucose tolerance test (GTT) and muscle strength testing.

### B. Background

Impairments in insulin secretion and glucose disposal affect a third of adults living in the United States (84 million, (CDC 2017)) and approximately 325 million people worldwide (IDF 2017). Over time, these symptoms progress into type 2 diabetes mellitus and then lead to secondary complications such as microvascular (e.g. diabetic nephropathy, retinopathy and neuropathy) and macrovascular (e.g. peripheral vascular and coronary artery disease) diseases.

Early investigations demonstrated a strong link between vitamin D and insulin secretion. In rats, studies had shown that vitamin D deficiency (diet induced) negatively affected insulin secretion (Kadowaki and Norman 1984; Norman et al. 1980). Later, 1,25(OH)2D3 was confirmed to increase insulin

secretion in the vitamin D-deficient rat model (Cade and Norman 1986). On the other hand, observational studies comparing serum 25(OH)D3 concentrations and diabetes, as well as randomized control trials with vitamin D3 supplementation, have not corroborated the link between vitamin D and insulin secretion (Mitri, Muraru, and Pittas 2011; Pittas et al. 2007, 2012, 2019; Wexler 2019). A recent longitudinal clinical trial, known as the Vitamin D and Type 2 Diabetes (D2d) Trial, studied the effects of supplementation with 4,000 IU of vitamin D3, the tolerable upper intake level (Ross et al. 2011), or placebo for 2.5 years in 2432 participants with pre-diabetes. The results of this trial indicated that vitamin D3 supplementation (n=1211) had no effect on the incidence of T2DM compared to the placebo group (n=1212) (Pittas et al. 2019). Many clinical trials have focused solely on the relationship between vitamin D3 intake or serum 25(OH)D3 and glucose metabolism and have established that vitamin D3 and 25(OH)D3 do not have an effect on insulin secretion. However, Bonakdaran and colleagues studied patients with chronic renal deficiency and found that 0.5 µg 1,25(OH)2D3, (n=13) given daily for 4 weeks improved glucose utilization compared to placebo-treated controls (n=14) (Bonakdaran et al. 2008). Thus, 1,25(OH)2D3 has been shown to positively affect insulin secretion in CKD patients and we believe that this benefit could be applied to persons with pre-diabetes. Based on these studies, we recognize that 1,25(OH)2D3 itself has a direct hormonal effect on pancreatic beta cells and insulin secretion and that administration of 1,25(OH)2D3, rather than vitamin D3 or 25(OH)D3, may be a key factor in improving glucose homeostasis.

Deficiency of vitamin D has been associated with muscle atrophy and poor diaphragm function (Dzik et al. 2019; Malinovschi et al. 2014). A recent study consisting of 4,157 older adults (>60 years) had shown that vitamin D deficiency (serum [25(OH)D] <30 nmol/L) was associated a three-fold increased incidence of impaired muscle performance and 2-fold increased incidence of impaired muscle strength compared to the vitamin D sufficient group (serum [25(OH)D] >50 nmol/L) (Aspell et al. 2019). Persons with diabetes are particularly susceptible to losses in muscle strength and endurance (Domaski and Ciechanowski 2012; Foley et al. 2007; Ijzerman et al. 2012). Poor muscle function not only accelerates deterioration of health and well-being, but it also impedes recovery following illness or hospitalization. In unpublished preliminary studies, [name] and colleagues have found that a mouse model severely deficient in 1,25(OH)2D3 experiences a 30% reduction in both muscle strength and fatigue after merely 2 weeks without exogenous 1,25(OH)2D3. Furthermore, our laboratory has shown that human muscle responds to 1,25(OH)2D3 stimulation by increasing mitochondrial function (Ryan et al. 2016). Thus, we believe that 1,25(OH)2D3 in the pre-diabetic populations will offer benefits in muscle function that will reduce losses in mobility and pulmonary diaphragm function.

The overall premise of this research is to investigate the action of a low daily dose of 1,25(OH)2D3 in pre-diabetic persons. Assuming that our hypothesis is valid, these individuals are likely to observe benefits from 1,25(OH)2D3 for improvements in insulin secretion, glucose metabolism, and muscle strength.

### C. Significance of Proposed Research

Insulin resistance is an early indication for the development of T2DM. The action of 1,25(OH)2D3 on insulin secretion and glucose utilization may delay or prevent the onset of T2DM in pre-diabetic persons. Additionally, The action of 1,25(OH)2D3 on muscle may maintain and improve muscle function.

## D. Design and Methods

### Study Design

We will compare insulin secretion and glucose uptake and muscle function before and after 8 weeks of treatment with 1,25(OH)2D3 or placebo in pre-diabetic participants. Men and women will be identified for recruitment to the study based on strict inclusion and exclusion criteria (Table 1 and *Enrollment Criteria*). After assignment to the study group, the participants will be randomly assigned on a first-come-first-serve basis to receive a daily oral tablet containing either 0.25 µg 1,25(OH)2D3 or placebo for 8 weeks. Before and after the intervention period, assessments will be made that will include a glucose tolerance test (GTT), knee flexor, and grip strength tests.

Table 1: Enrollment Groups

Group	Criteria
1	Men
2	Pre-menopausal Women

### Enrollment Criteria

#### Inclusion criteria:

- Adults, 20 - 45 years old
- Body mass index (BMI) of >24 kg/m^2
- Fasting serum glucose <126 mg/dl

#### Exclusion criteria:

- BMI ≤24 kg/m^2
- Fasting serum glucose ≥126 mg/dl
- Currently taking calcium and/or vitamin D supplements and unwilling to stop for study duration
- Serum total calcium >10.2 mg/dL
- Serum inorganic phosphorus >4.5 mg/dL
- Pregnancy or breastfeeding
- Diagnosis of Diabetes Mellitus
- Diagnosis of Rheumatoid Arthritis
- Diagnosis of Chronic Obstructive Pulmonary Disease (COPD)
- Renal insufficiency/failure (serum creatinine >1.5 mg/dl men, >1.3 mg/dl women)
- Chronic active liver disease (bilirubin > 1.2 mg/dL, AST >144 IU/L, or ALT >165 IU/L)
- History of chronic hepatitis
- **History of depression, anxiety or psychiatric disease**
- Active coronary artery disease (unstable angina, myocardial infarction, stroke, and revascularization of coronary, peripheral or carotid artery within 3 months of recruitment)
- Oral warfarin or history of blood clotting disorders
- Platelet count < 100,000 per uL within the last 7 days
- Alcohol consumption greater than 2 glasses/day or other substance abuse
- Untreated or uncontrolled thyroid disorders (outside a TSH range of 0.5 to 10 mIU/L)
- Debilitating chronic disease (at the discretion of the investigators)

- The presence of infections, highly communicable diseases (AIDS, active tuberculosis, venereal disease, hepatitis)
- Any malignancy

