## Consent and Screening

Potential participants will report to the Clinical Research and Trials Unit at the Charlton Building or St. Mary's Hospital. A member of the study team will meet the potential participant and then the consent form will be read and discussed in a private area. After receiving consent, the participant will have a urine pregnancy test (if applicable) and screening blood work (fasted). Screening blood work will be processed in a clinical lab and will include: Basic Metabolic Panel (sodium, potassium, bicarbonate, creatinine, BUN, calcium, phosphorous, and albumin), ALT (alanine transaminase), AST (aspartate aminotransaminase), BILIT (total bilirubin), TSH (thyroid stimulating hormone), CBC with differential count including platelets, APT (activated partial thromboplastin time), PT (prothrombin time), GLUCF (glucose fasting) and CDHVD (1,25(OH)2D3, 25(OH)D3). Participants will have a nursing assessment that will include vital signs and a brief physical exam by a study MD.

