**Lower Extremity Strength Test:** Participants will undergo measurements at the Motion Analysis Laboratory. Dominant knee flexor musculature strength will be assessed via a computerized multi-joint testing system (Humac Norm System; CSMi Medical Solutions Stoughton, MA). Subjects will be positioned and stabilized on the testing apparatus using standardized protocols. The axis of the knee joint will be aligned with the center of rotation of the dynamometer arm and the lower leg will be strapped to the lever arm just proximal to the angle. Participants will be buckled in at the waist, shoulders and the distal part of the thigh. Peak torque will be assessed at a knee angle of 60° flexion. Participants will be verbally encouraged to perform at their maximum. Torque generated by the subject in an isometric contraction will be measured and recorded. Three isometric strength testing repetitions will be performed for each muscle group. Each isometric muscle contraction will be held for 5s and a 30s rest period will be observed between contractions. The largest value from three trials will be used.

Upper Extremity Strength Test: Isometric handgrip strength will be measured in the Motion Analysis Laboratory. Dominant hand grip strength will be tested using a custom designed digital grip dynamometer (NK Biotechnical Engineering Co., Minneapolis, MN). The measurements will be performed with participants sitting upright, feet flat on the floor, elbow flexed to 90°, and forearm in neutral position. Standardized verbal encouragement will be given for each contraction. Three maximal repetitions (30s rest between attempts) will be recorded. The largest value from three trials will be used.

Table 2: Timeline of the study

Consent, Screening, and Baseline Assessments (complete within 5 days)	
Day 1	Consent and Screening Completion of the PROMIS 10 Questionnaire Food Frequency Questionnaire Nutrition Consult with Dietitian Urinalysis (women only) 
 
• HCG
 
 Fasting Blood Draw 
 
• Basic Metabolic Panel, ALT, AST, BILIT, TSH, CBC, APT, PT, GLUCF, PTH, CDHVD (1,25(OH)2D3, 25(OH)D3), calcium, and phosphorus
 

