Day 2	Glucose Tolerance Test 
 
• Glucose, insulin, glucagon and C-peptide, at fasting and at 10, 20, 30, 60, 90 and 120 minutes following oral glucose bolus
 
 Knee Flexor Strength Test Grip Strength Test Physical Exam with Physician Begin Intervention with 1,25(OH)2D3 or Placebo
Intervention	
Week 2	Blood Draw: calcium and phosphorus
Week 4	Blood Draw: calcium and phosphorus
Week 6	Blood Draw: calcium and phosphorus
Week 8	Begin Post-Intervention Assessments
Post-Intervention Assessments (complete within 2 days of taking last tablet )	
Day 1	Fasting Blood Draw 
 
• CDHVD (1,25(OH)2D3), calcium, and phosphorus
 
 Glucose Tolerance Test 
 
• Glucose, insulin, glucagon and C-peptide, at fasting and at 10, 20, 30, 60, 90 and 120 minutes following oral glucose bolus
 
 Knee Flexor Strength Test Grip Strength Test Completion of PROMIS 10 Questionnaire

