### Human Subjects

#### Risks to the subjects

Human Subjects Involvement and Characteristics: All protocols and all techniques to be used will be approved by the Mayo Clinic Institutional Review Board (IRB) prior to initiation of any studies. Subject characteristics and inclusion/exclusion criteria have been clearly specified above. Our plan is to complete the study on 50 participants with 25 in each group. We are anticipating a target accrual of 75 subjects to account for anticipated dropout in order to have 50 participants complete the study.

Sources of Materials. Samples of blood and urine obtained during the study will be used exclusively for research purposes. No use will be made of pre-existing specimens.

Urine: Urine samples will be collected from women for pregnancy testing.

Blood: One blood draw will occur during the screening visit (approximately 15 mL). A glucose tolerance test will be performed at baseline that will include seven blood draws (approximately 1 mL of blood from each draw) periodically over the course of 2 hours. Every 2 weeks during the intervention, a small sample of blood (1 mL) will be collected to monitor calcium and phosphorus levels. At completion of 8 weeks of intervention, another GTT will be performed and 5 mL of blood will be collected for post-intervention analysis. This analysis will include calcium, phosphorus, 25(OH)D $_3$ , 25(OH)D $_2$ , 1,25(OH) $_2$ D $_3$ , and 1,25(OH) $_2$ D $_2$ . All specimens will be processed internally and stored in the study team laboratory.

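### Pregnancy is excluded at entry, but no scheduled test after Day 1 maintains that exclusion through the 8 weeks of dosing

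*Combined protocol and SAP*

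**What the plan says.** The exclusion list contains "Pregnancy or breastfeeding". Table 1 (Study Design) defines two enrolment groups, men and "Pre-menopausal Women", with no quota for either. The age criterion is "Adults, 20 - 45 years old".

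Consent and Screening provides for a urine pregnancy test, where applicable, after consent. Table 2 lists it once, as a urine HCG for women on Day 1. Consent, screening and baseline share a 5-day window, and the first tablet follows the baseline assessments. Under Risks to the subjects, the protocol adds that "Urine samples will be collected from women for pregnancy testing", without giving timing or frequency.

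During dosing, the entry in Table 2 for each of weeks 2, 4 and 6 is "Blood Draw: calcium and phosphorus". The post-intervention day lists a fasting draw, GTT, two strength tests and the PROMIS 10, with no HCG.

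The only written rule for taking a participant off the intervention, under Adequacy of Protection Against Risks, concerns calcium or phosphorus above the upper limit of normal. Neither criteria list mentions contraception. Section F does not say how the data of a participant who becomes pregnant are analysed.

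**The concern.** The protocol treats pregnancy as incompatible with entering the trial but schedules no check that this remains true during treatment. A woman whose pregnancy is too early for the Day 1 test, or who conceives afterwards, could continue daily tablets and the 400 mg calcium diet with no scheduled test to show it.

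The protocol handles other entry criteria differently. Raised serum calcium and phosphorus are exclusions, are rechecked every two weeks and carry an off-intervention rule. The supplement criterion runs for the whole study. Pregnancy is checked once, and no reason is given for the difference.

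The main stake is exposure during pregnancy that the plan's own exclusion would have prevented at entry. A lesser stake is the data. The primary endpoint is completion of the final blood collection and GTT, so such a participant would count as a completer. Her disposition index (DI), φ and insulin action would then be analysed with no rule for including or setting them aside.

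**Working it through.** **1. Schedule, side by side**

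| Time point | Calcium and phosphorus | Pregnancy test |
|---|---|---|
| Day 1 (screening) | yes | urine HCG |
| Weeks 2, 4, 6 | yes | none listed |
| Post-intervention day (week 8) | yes | none listed |
| Written off-intervention rule | yes | none |

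With a 5-day window, a Day 1 test can precede the first tablet by up to 5 − 1 = 4 days.

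**2. Expected conceptions during dosing**

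The documents give no pregnancy rate and no sex split, so both are assumed. For the number of women I take half of the 50 planned completers (25) and half of the target accrual of 75 (37.5, taken as 37). For the annual conception rate r, I take 3% to 10%.

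The 8-week probability is p = 1 − (1 − r)^(8/52).
- r = 3%: p = 0.0047
- r = 10%: p = 0.0161

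The expected number is n × p, and the chance of at least one is 1 − (1 − p)^n.

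| Women | r | Expected | Chance of at least one |
|---|---|---|---|
| 25 | 3% | 0.12 | 11% |
| 25 | 10% | 0.40 | 33% |
| 37 | 3% | 0.17 | 16% |
| 37 | 10% | 0.59 | 45% |

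With 1:1 allocation about half would be on active drug: 0.12/2 = 0.06 to 0.59/2 = 0.30. A wider range of r, 1% to 20% with 25 women, gives 0.04 to 0.84 expected. These figures exclude pregnancies already present but too early to show on Day 1. They give every woman the full 8 weeks, which overstates the count for those who drop out.

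**3. Effect on the arm comparison**

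Table 3 first. For DI (mean 1920, SD 321), a 20% difference is 0.20 × 1920 = 384. A two-sample t-test with 85% power and an assumed two-sided alpha of 0.05 needs 13.6 per arm, so 14 per arm and 28 in total. For φ (63.8, SD 7.5) the total is 14.6, so 15. Both match the plan, and neither figure is in dispute.

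The documents give no effect of pregnancy on DI, so a shift is assumed for one participant in an arm of 25.
- 1 SD: 321/25 = 12.84, and 12.84/384 = 3.3% of the target difference
- 2 SD: 25.68/384 = 6.7%

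Setting aside three of the 50 completers takes DI power from 98.5% to 98.0%.

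**The case against.** The strongest objection is that the protocol is consistent with itself: pregnancy is an enrolment exclusion and is tested at enrolment. That stands. A reader might infer that the exclusion list and Table 2 contradict each other, but they do not. The gap is that the exclusion is not carried forward.

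A reader might also infer that an on-study pregnancy would go undetected. The documents do not support that. Participants attend at weeks 2, 4 and 6 and can reach an investigator or on-call physician at any hour, so a woman could report a pregnancy. What can be said is that no scheduled test would find it.

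A third inference, that such a pregnancy alters the week-8 GTT, is not supported as fact. No section gives a size or direction for the effect. It could confound one participant's result, but under the assumed shifts the arm comparison and power barely move.

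Nor can it be concluded that the trial has no contraception or pregnancy-reporting provision. Consent pages are not in the text available for review, and the Data Safety and Monitoring Plan is cited but not reproduced, so either may contain one.

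These limits narrow the point. They do not answer it: in the protocol's schedule, the Day 1 test is the last.

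**Conclusion.** The point holds as a gap in maintaining eligibility and safety during dosing. The entry exclusion is tested once and then not followed for 8 weeks, unlike the calcium and phosphorus exclusions. About 0.1 to 0.6 conceptions are expected over the dosing period, about half on active drug, given the assumed 25 to 37 women and annual rates of 3 to 10%. That is fewer than one case, but at the upper end the chance of at least one is 45%, enough to justify a written provision.

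The statistical consequence is minor: roughly 3 to 7% of the target DI difference for one affected participant under an assumed 1 to 2 SD shift. The case for change rests on safety, with the missing analysis rule second.

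**What to change.** Bring the exclusion list, Table 2 and the off-intervention paragraph under Adequacy of Protection Against Risks into line, so that pregnancy status is rechecked during the intervention at visits already scheduled. In section F, state in advance how the GTT data of a participant who becomes pregnant are analysed, and whether she counts as a completer for the primary endpoint.

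Which visits carry the test, whether contraception is required and how a positive result is handled clinically are for the sponsor and IRB. If the consent form or the Data Safety and Monitoring Plan already covers any of this, a cross-reference in the protocol is enough for that part.

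The cost is a few urine strips per woman, a few sentences of text and possibly the loss of an occasional participant. The power figures above show that such losses are affordable. A recheck would still miss a conception too recent to show at that visit, so it narrows the gap without closing it.

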## Recruitment

A study coordinator will work closely with [name] to identify potential candidates for this study. Participants will be recruited from the Research Studies section of the Mayo Classifieds website, and from participants who completed other research studies and agreed to be contacted again for other studies. While most of the information will be provided to potential participants in person, participants may also be contacted by telephone with a brief description of the study and to determine if they are interested in participating. The study coordinator will perform a brief screening questionnaire to determine eligibility to proceed with enrollment. The information gathered from the screening questionnaire will not be stored or used for data analysis if participants do not qualify for the study.

## Consent and Screening

Potential participants will report to the Clinical Research and Trials Unit at the Charlton Building or St. Mary's Hospital. A member of the study team will meet the potential participant and then the consent form will be read and discussed in a private area. After receiving consent, the participant will have a urine pregnancy test (if applicable) and screening blood work (fasted). Screening blood work will be processed in a clinical lab and will include: Basic Metabolic Panel (sodium, potassium, bicarbonate, creatinine, BUN, calcium, phosphorous, and albumin), ALT (alanine transaminase), AST (aspartate aminotransaminase), BILIT (total bilirubin), TSH (thyroid stimulating hormone), CBC with differential count including platelets, APT (activated partial thromboplastin time), PT (prothrombin time), GLUCF (glucose fasting) and CDHVD (1,25(OH)2D3, 25(OH)D3). Participants will have a nursing assessment that will include vital signs and a brief physical exam by a study MD.

## Study Intervention Agent: 1,25-Dihydroxyvitamin D3

As per DrugBank, this agent is used to treat refractory rickets (vitamin D resistant rickets), familial hypophosphatemia, hypoparathyroidism, and in the management of hypocalcemia and renal osteodystrophy in patients with chronic renal failure undergoing dialysis. This protocol will use doses that are identical to those used for these other clinical indications.

The Mayo Clinic Pharmacy will prepare 1,25(OH)2D3 tablets containing 0.25 µg of 1,25(OH)2D3 as well as an identical placebo tablet containing 0 µg of 1,25(OH)2D3. Assignment will remain blinded to participant, healthcare providers and members of the study team who have direct participant contact.

Intervention instructions: During screening and prior to receiving the intervention, caloric intake and vitamin and mineral analysis will be estimated by having participants complete the VIOCARE Food Frequency questionnaire, with the dieticians in the clinical research unit. A dietician will instruct the participant to adhere to a diet of 400 mg calcium and 800-1000 mg phosphorus while taking 1,25(OH)2D3/placebo agent intervention. These instructions are included to prevent potential development of hypercalcemia and/or hyperphosphatemia as a direct result of 1,25(OH)2D3. After completing screening and baseline assessments, participants will be instructed to take 1 tablet (containing 0.25 µg 1,25(OH)2D3 or placebo) per day for 8 weeks following the completion of Day 3 of baseline assessments (Table 2).

